10.1.2 Financial Disclosure

Financial disclosure requirements are outlined in the US Food and Drug Administration Regulations, Financial Disclosure by Clinical Investigators (21 CFR Part 54). It is the Sponsor's responsibility to determine, based on these regulations, whether a request for financial disclosure information is required. It is the investigator's/subinvestigator's responsibility to comply with any such request.

The investigator/subinvestigator(s) agree, if requested by the Sponsor in accordance with 21 CFR Part 54, to provide his/her financial interests in and/or arrangements with the Sponsor to allow for the submission of complete and accurate certification and disclosure statements. The investigator/subinvestigator(s) further agree to provide this information on a Certification/Disclosure Form, frequently known as a financial disclosure form, provided by the Sponsor. The investigator/subinvestigator(s) also consent to the transmission of this information to the Sponsor in the United States for these purposes. This may involve the transmission of information to countries that do not have laws protecting personal data.

Data Protection

10.1.3

The Sponsor will conduct this study in compliance with all applicable data protection regulations.

Participants will be assigned a unique identifier by the Sponsor. Any participant records or datasets that are transferred to the Sponsor will contain the identifier only; participant names or any information that would make the participant identifiable will not be transferred.

The participant must be informed that his/her personal study-related data will be used by the Sponsor in accordance with local data protection law. The level of disclosure must also be explained to the participant.

The participant must be informed that his/her medical records may be examined by Clinical Quality Assurance auditors or other authorized personnel appointed by the Sponsor, by appropriate IRB/IEC members, and by inspectors from regulatory authorities.

10.1.3.1 Confidentiality of Data

By signing this protocol, the investigator affirms to the Sponsor that information furnished to the investigator by the Sponsor will be maintained in confidence, and such information will be divulged to the IRB, IEC, or similar or expert committee; affiliated institution and employees, only under an appropriate understanding of confidentiality with such board or committee, affiliated institution and employees. Data generated by this study will be considered confidential by the investigator, except to the extent that it is included in a publication as provided in the Publications section of this protocol.

10.1.3.2 Confidentiality of Participant Records

By signing this protocol, the investigator agrees that the Sponsor (or Sponsor representative), IRB/IEC, or regulatory authority representatives may consult and/or copy study documents to verify worksheet/CRF data. By signing the consent form, the participant agrees to this process. If study documents will be photocopied during the process of verifying worksheet/CRF information, the participant will be identified by unique code only; full names/initials will be masked before transmission to the Sponsor.

By signing this protocol, the investigator agrees to treat all participant data used and disclosed in connection with this study in accordance with all applicable privacy laws, rules and regulations.

10.1.3.3 Confidentiality of IRB/IEC Information

The Sponsor is required to record the name and address of each IRB/IEC that reviews and approves this study. The Sponsor is also required to document that each IRB/IEC meets regulatory and ICH GCP requirements by requesting and maintaining records of the names and qualifications of the IRB/IEC members and to make these records available for regulatory agency review upon request by those agencies.

10.1.4 Committees Structure

This section is not applicable as there are no study governance committees.

10.1.5 Publication Policy

The results of this study may be published or presented at scientific meetings. The Sponsor will comply with the requirements for publication of study results. In accordance with standard editorial and ethical practice, the Sponsor will generally support publication of multicenter studies only in their entirety and not as individual site data. In this case, a coordinating investigator will be designated by mutual agreement.

If publication activity is not directed by the Sponsor, the investigator agrees to submit all manuscripts or abstracts to the Sponsor before submission. This allows the Sponsor to protect proprietary information and to provide comments.

Authorship will be determined by mutual agreement and in line with ICMJE authorship requirements.

10.1.6 Compliance with Study Registration and Results Posting Requirements

Under the terms of the FDAAA of 2007 and the EMA clinical trial Directive 2001/20/EC, the Sponsor of the study is solely responsible for determining whether the study and its results are subject to the requirements for submission to http://www.clinicaltrials.gov, www.clinicaltrialsregister.eu or other local registries. MSD, as Sponsor of this study, will review this protocol and submit the information necessary to fulfill these requirements. MSD entries are not limited to FDAAA or the EMA clinical trials directive mandated trials. Information posted will allow participants to identify potentially appropriate studies for their disease conditions and pursue participation by calling a central contact number for further information on appropriate study locations and study-site contact information.

By signing this protocol, the investigator acknowledges that the statutory obligations under FDAAA, the EMA clinical trials directive, or other locally mandated registries are that of the Sponsor and agrees not to submit any information about this study or its results to those registries.

10.1.7 Compliance with Law, Audit, and Debarment

By signing this protocol, the investigator agrees to conduct the study in an efficient and diligent manner and in conformance with this protocol; generally accepted standards of GCP (eg, ICH GCP: Consolidated Guideline and other generally accepted standards of GCP); and all applicable federal, state and local laws, rules and regulations relating to the conduct of the clinical study.

The Code of Conduct, a collection of goals and considerations that govern the ethical and scientific conduct of clinical investigations sponsored by MSD, is provided in this appendix under the Code of Conduct for Clinical Trials.

The investigator agrees not to seek reimbursement from participants, their insurance providers, or from government programs for procedures included as part of the study reimbursed to the investigator by the Sponsor.

The investigator will promptly inform the Sponsor of any regulatory authority inspection conducted for this study.

The investigator agrees to provide the Sponsor with relevant information from inspection observations/findings to allow the Sponsor to assist in responding to any citations resulting from regulatory authority inspection and will provide the Sponsor with a copy of the proposed response for consultation before submission to the regulatory authority.

Persons debarred from conducting or working on clinical studies by any court or regulatory authority will not be allowed to conduct or work on this Sponsor's studies. The investigator will immediately disclose in writing to the Sponsor if any person who is involved in conducting the study is debarred or if any proceeding for debarment is pending or, to the best of the investigator's knowledge, threatened.

10.1.8 Data Quality Assurance

All participant data relating to the study will be recorded on printed or electronic CRF unless transmitted to the Sponsor or designee electronically (eg, laboratory data). The investigator or qualified designee is responsible for verifying that data entries are accurate and correct by physically or electronically signing the CRF.

Detailed information regarding Data Management procedures for this protocol will be provided separately.

The investigator must maintain accurate documentation (source data) that supports the information entered in the CRF.

The investigator must permit study-related monitoring, audits, IRB/IEC review, and regulatory agency inspections and provide direct access to source data documents.

Study documentation will be promptly and fully disclosed to the Sponsor by the investigator upon request and also shall be made available at the study site upon request for inspection, copying, review, and audit at reasonable times by representatives of the Sponsor or any regulatory authorities. The investigator agrees to promptly take any reasonable steps that are requested by the Sponsor or any regulatory authorities as a result of an audit or inspection to cure deficiencies in the study documentation and worksheets/CRFs.

The Sponsor or designee is responsible for the data management of this study including quality checking of the data.

Study monitors will perform ongoing source data review and verification to confirm that data entered into the CRF by authorized site personnel are accurate, complete, and verifiable from source documents; that the safety and rights of participants are being protected; and that the

study is being conducted in accordance with the currently approved protocol and any other study agreements, ICH GCP, and all applicable regulatory requirements.

Records and documents, including participants' documented informed consent, pertaining to the conduct of this study must be retained by the investigator for 15 years after study completion unless local regulations or institutional policies require a longer retention period. No records may be destroyed during the retention period without the written approval of the Sponsor. No records may be transferred to another location or party without written notification to the Sponsor.

10.1.9 Source Documents

Source documents provide evidence for the existence of the participant and substantiate the integrity of the data collected. The investigator/institution should maintain adequate and accurate source documents and study records that include all pertinent observations on each of the site's participants. Source documents and data should be attributable, legible, contemporaneous, original, accurate, and complete. Changes to source data should be traceable, should not obscure the original entry, and should be explained if necessary (eg, via an audit trail). Source documents are filed at the investigator's site.

Data reported on the CRF or entered in the eCRF that are transcribed from source documents must be consistent with the source documents or the discrepancies must be explained. The investigator/institution may need to request previous medical records or transfer records, depending on the study. Also, current medical records must be available.

10.1.10 Study and Site Closure

The Sponsor or its designee may stop the study or study-site participation in the study for medical, safety, regulatory, administrative, or other reasons consistent with applicable laws, regulations, and GCP.

In the event the Sponsor prematurely terminates a particular study site, the Sponsor or designee will promptly notify that study site's IRB/IEC as specified by applicable regulatory requirement(s).

MK-6194-008-04 FINAL PROTOCOL

PRODUCT: MK-6194
PROTOCOL/AMENDMENT NO.: 008-04

10.2 Appendix 2: Clinical Laboratory Tests

- The tests detailed in Table 7 will be performed by the central laboratory.
- Local laboratory results are only required in the event that the central laboratory results are not available in time for either study intervention administration and/or response evaluation. If a local sample is required, it is important that the sample for central analysis is obtained at the same time. Additionally, if the local laboratory results are used to make either a study intervention decision or response evaluation, the results must be entered into the CRF.
- Protocol-specific requirements for inclusion or exclusion of participants are detailed in Section 5 of the protocol.
- Additional tests may be performed at any time during the study as determined necessary by the investigator or required by local regulations.

Table 7 Protocol-required Safety Laboratory Assessments

Laboratory Assessments	Parameters						
Hematology	Platelet Count		RBC Indices:		WBC count with		
	RBC Count		MCV	4CV		Differential:	
	Hemoglobin		MCH		Neutrophils		
	Hematocrit		Reticulocytes		Lymphocytes		
					Monocytes		
					Eosinophils		
					Basophils		
Chemistry	BUN Potass		sium AST/SGOT			Total bilirubin	
						(and direct	
						bilirubin, if total	
						bilirubin is	
						above the ULN)	
	Albumin	Bicar	bonate	Chloride		Phosphorous	
	Creatinine	Sodium		ALT/SGPT		Total Protein	
	Glucose	Calci	um	Alkaline		LDH	
				phosphatase			
	Immunoglobulin E	CRP					
	(IgE)						
Routine Urinalysis	Specific gravity						
	• pH, glucose, protein, blood, ketones, [bilirubin, urobilinogen, nitrite, leukocyte esterase] by dipstick						
	Microscopic examination (if blood or protein is abnormal)						
Pregnancy Testing	Highly sensitive serum or urine hCG pregnancy test (as needed for WOCBP)						

PRODUCT: MK-6194

PROTOCOL/AMENDMENT NO.: 008-04

Laboratory Assessments	Parameters
Assessments Other Screening Tests	 Coagulation: PT and INR, aPTT FSH (as needed in WONCBP only) Urine drug screen (to include at minimum: amphetamines, barbiturates, cocaine, opiates, cannabinoids and benzodiazepines) Alcohol test Serology (HIV antibody, HBsAg, HBsAb, HBcAb, and hepatitis C virus antibody) per site SOP Purified protein derivation (PPD test or QuantiFERON®-TB Gold test All study-required laboratory assessments will be performed by a central
	laboratory, except pregnancy tests, TB test, Urine Drug Screen (UDS), and alcohol test, which may be performed centrally or locally.

ALT=alanine aminotransferase; AST=aspartate aminotransferase; BUN=blood urea nitrogen; FSH=follicle-stimulating hormone; [HBsAg=hepatitis B surface antigen]; hCG=human chorionic gonadotropin; [HIV=human immunodeficiency virus]; MCH=mean corpuscular hemoglobin; MCV=mean corpuscular volume; RBC=red blood cell; SGOT=serum glutamic-oxaloacetic transaminase; SGPT=serum glutamic-pyruvic transaminase; ULN=upper limit of normal; WBC=white blood cell; WOCBP=women of childbearing potential

The investigator (or medically qualified designee) must document their review of each laboratory safety report.

92

10.3 Appendix 3: Adverse Events: Definitions and Procedures for Recording, Evaluating, Follow-up, and Reporting

10.3.1 Definitions of Medication Error, Misuse, and Abuse

Medication Error

This is an unintended failure in the drug treatment process that leads to or has the potential to lead to harm to the patient.

Misuse

This refers to situations where the medicinal product is intentionally and inappropriately used not in accordance with the terms of the product information.

Abuse

This corresponds to the persistent or sporadic, intentional excessive use of a medicinal product for a perceived psychological or physiological reward or desired non-therapeutic effect.

10.3.2 Definition of AE

AE definition

- An AE is any untoward medical occurrence in a clinical study participant, temporally
 associated with the use of study intervention, whether or not considered related to the
 study intervention.
- Note: An AE can therefore be any unfavorable and unintended sign (including an abnormal laboratory finding), symptom, or disease (new or exacerbated) temporally associated with the use of a study intervention.
- Note: For purposes of AE definition, study intervention (also referred to as Sponsor's product) includes any pharmaceutical product, biological product, vaccine, diagnostic agent, medical device, combination product, or protocol specified procedure whether investigational or marketed (including placebo, active comparator product, or run-in intervention), manufactured by, licensed by, provided by, or distributed by the Sponsor for human use in this study.

Events meeting the AE definition

• Any abnormal laboratory test results (hematology, clinical chemistry, or urinalysis) or other safety assessments (eg, ECG, radiological scans, vital signs measurements), including those that worsen from baseline, considered clinically significant in the medical and scientific judgment of the investigator.

PRODUCT: MK-6194 93

Exacerbation of a chronic or intermittent preexisting condition including either an increase in frequency and/or intensity of the condition.

- New conditions detected or diagnosed after study intervention administration even though it may have been present before the start of the study.
- Signs, symptoms, or the clinical sequelae of a suspected drug-drug interaction.
- Signs, symptoms, or the clinical sequelae of a suspected overdose of either study intervention or a concomitant medication.
- For all reports of overdose (whether accidental or intentional) with an associated AE, the AE term should reflect the clinical symptoms or abnormal test result. An overdose without any associated clinical symptoms or abnormal laboratory results is reported using the terminology "accidental or intentional overdose without adverse effect."
- Any new cancer or progression of existing cancer

Events NOT meeting the AE definition

- Medical or surgical procedure (eg, endoscopy, appendectomy): the condition that leads to the procedure is the AE.
- Situations in which an untoward medical occurrence did not occur (social and/or convenience admission to a hospital).
- Anticipated day-to-day fluctuations of preexisting disease(s) or condition(s) present or detected at the start of the study that do not worsen.
- Surgical procedure(s) planned prior to informed consent to treat a preexisting condition that has not worsened.
- Refer to Section 8.4.6 for protocol-specific exceptions.

10.3.3 **Definition of SAE**

If an event is not an AE per definition above, then it cannot be an SAE even if serious conditions are met.

An SAE is defined as any untoward medical occurrence that, at any dose:

a. Results in death

b. Is life-threatening

MK-6194-008-04 FINAL PROTOCOL

The term "life-threatening" in the definition of "serious" refers to an event in which the participant was at risk of death at the time of the event. It does not refer to an event, which hypothetically might have caused death, if it were more severe.

c. Requires inpatient hospitalization or prolongation of existing hospitalization

Hospitalization is defined as an inpatient admission, regardless of length of stay, even if the hospitalization is a precautionary measure for continued observation. (Note: Hospitalization for an elective procedure to treat a preexisting condition that has not worsened is not an SAE.) A preexisting condition is a clinical condition that is diagnosed prior to the use of an MSD product and is documented in the participant's medical history.

d. Results in persistent or significant disability/incapacity

- The term disability means a substantial disruption of a person's ability to conduct normal life functions.
- This definition is not intended to include experiences of relatively minor medical significance such as uncomplicated headache, nausea, vomiting, diarrhea, influenza, and accidental trauma (eg, sprained ankle) that may interfere with or prevent everyday life functions but do not constitute a substantial disruption.

e. Is a congenital anomaly/birth defect

• In offspring of participant taking the product regardless of time to diagnosis.

f. Other important medical events

- Medical or scientific judgment should be exercised in deciding whether SAE
 reporting is appropriate in other situations such as important medical events that may
 not be immediately life-threatening or result in death or hospitalization but may
 jeopardize the participant or may require medical or surgical intervention to prevent 1
 of the other outcomes listed in the above definition. These events should usually be
 considered serious.
- Examples of such events include invasive or malignant cancers, intensive treatment in an emergency room or at home for allergic bronchospasm, blood dyscrasias or convulsions that do not result in hospitalization, or development of drug dependency or drug abuse.

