3 HYPOTHESES, OBJECTIVES, AND ENDPOINTS

Hypotheses are aligned with objectives in the Objectives and Endpoints table.

This study is to be conducted in adult participants with moderate to severe atopic dermatitis.

[figure not shown]
Objectives	Endpoints						
Primary							
To evaluate the safety and tolerability of MK-6194 in participants with atopic dermatitis, following multiple dose subcutaneous administration.	AEs, discontinuation from dosing due to AEs						
Secondary							
To characterize serum PK for MK-6194 in participants with atopic dermatitis following multiple dose subcutaneous administration.	·						

Objectives	Endpoints
To characterize regulatory T-cell pharmacodynamics of MK-6194 in participants with atopic dermatitis following multiple dose subcutaneous administration. CCI CCI CCI	Immunophenotyping of Tregs
Tertiary/Exploratory	
Measures of Treatment Response	CCI
To assess emerging biomarkers of atopic dermatitis disease activity.	
To identify molecular (genomic, and/or proteomic) biomarkers that may be indicative of clinical response/resistance, pharmacodynamic activity and/or the mechanism of action of MK-6194.	Blood and/or skin biopsy biomarker parameters that may include but are not limited to DNA, RNA, protein-based analyses.

	Objectives	Endpoints
•	To characterize immunogenicity of MK-6194 in participants with atopic dermatitis following multiple dose subcutaneous administration	• ADA titers
•	To explore the relationship between genetic variation and response to MK-6194 administration in relation to the recorded PK, pharmacodynamics, and clinical data.	Germline genetic variation and association to PK, pharmacodynamics, and clinical data collected in this study
•	To explore the relationship between genetic variation and response to the treatment(s) administered, and mechanisms of disease. Variation across the human genome may be analyzed for association with clinical data collected in the study.	Germline genetic variation and association to clinical data collected in this study.

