7 DISCONTINUATION OF STUDY INTERVENTION AND PARTICIPANT WITHDRAWAL

7.1 Discontinuation of Study Intervention

Discontinuation of study intervention does not represent withdrawal from the study. As certain data on clinical events beyond study intervention discontinuation may be important to the study, they must be collected through the participant's last scheduled follow-up, even if the participant has discontinued study intervention. Therefore, all participants who discontinue study intervention before completion of the protocol-specified treatment period will still continue to participate in the study as specified in Section 1.3 and Section 8.1.9, or if available, a PCL.

Participants may discontinue study intervention at any time for any reason or be discontinued from the study intervention at the discretion of the investigator should any untoward effect occur. In addition, a participant may be discontinued from study intervention by the investigator or the Sponsor if study intervention is inappropriate, the study plan is violated, or for administrative and/or other safety reasons. Specific details regarding procedures to be performed at study intervention discontinuation are provided in Section 8.1.9.

A participant must be discontinued from study intervention, but continue to be monitored in the study, for any of the following reasons:

- The participant or participant's legally acceptable representative requests to discontinue study intervention.
- Participants who receive a systemic rescue treatment or phototherapy
 - Note: Participants who use topical corticosteroids prior to Week 6 will be permitted to continue in the study.
- The participant's treatment assignment has been unblinded by the investigator, MSD subsidiary, or through the emergency unblinding call center.
- The participant missed four doses of study intervention within the first eight weeks of the study.
- The participant has a Grade 3 or higher AE (Grade 2 or higher for the system-organ class of Cardiac Disorders) considered related to study intervention.
- The participant has a medical condition or personal circumstance which, in the opinion of the investigator and/or Sponsor, placed the participant at unnecessary risk from continued administration of study intervention.

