8.4.6 Disease-related Events and/or Disease-related Outcomes Not Qualifying as AEs or SAEs

Disease-related events and/or disease-related outcomes not qualifying as AEs or SAEs are not applicable to this study.

MK-6194-008-04 FINAL PROTOCOL

PRODUCT: MK-6194

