9.6 Statistical Methods

Primary Analysis

Safety: Incidence of adverse experiences will be descriptively summarized. Summary statistics and plots will be generated for the change from baseline values either be computed on original scale (raw change from baseline) or on the log-scale and back-transformed for reporting (percent change from baseline) in the incidence of AEs and discontinue of dosing due to AEs, as deemed clinically appropriate.

Secondary Analysis

Exploratory Analysis

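### Worsening of atopic dermatitis counts as an AE and is not summarised separately, so more flares on placebo could narrow or hide a drug excess in any-AE incidence

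*Combined protocol and SAP*

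**What the plan says.** Section 3 gives the primary endpoints as "AEs, discontinuation from dosing due to AEs". Section 9.4 lists AEs only, although 9.6 also covers discontinuation. The visible primary analysis in 9.6 is "Incidence of adverse experiences will be descriptively summarized". It has no test and no separate line for AD worsening.

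Section 10.3.2 lists as an AE "Exacerbation of a chronic or intermittent preexisting condition including either an increase in frequency and/or intensity of the condition". It excludes "Anticipated day-to-day fluctuations of preexisting disease(s) or condition(s) present or detected at the start of the study that do not worsen" and refers to Section 8.4.6 for protocol-specific exceptions. That section says: "Disease-related events and/or disease-related outcomes not qualifying as AEs or SAEs are not applicable to this study".

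Section 7.1 names, among the reasons for mandatory and permanent discontinuation of dosing, "Participants who receive a systemic rescue treatment or phototherapy", with the note that "Participants who use topical corticosteroids prior to Week 6 will be permitted to continue in the study". A separate item in the same list is AE-based: "The participant has a Grade 3 or higher AE (Grade 2 or higher for the system-organ class of Cardiac Disorders) considered related to study intervention".

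Section 4.2.2 says that placebo is there so that the safety data can be properly assessed, and to keep the blind. Section 2.2 describes AD as relapsing and says that MK-6194 may bring a significant and lasting benefit.

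**The concern.** The safety question is whether participants on drug have more adverse events than those on placebo. In this trial one class of event, worsening of the treated disease, should become less frequent if the drug works. Counting it together with other AEs puts a possible benefit and a possible harm into the same proportion, with opposite signs. The any-AE contrast can then look reassuring because placebo participants flared, and not because the drug was well tolerated.

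Tables by event term would not fully resolve this. The published 9.6 does not commit to them. If they were produced, they would show one term at a time and would not give the number of participants with at least one AE other than AD worsening.

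The discontinuation endpoint raises a narrower question. A flare that leads to systemic rescue ends dosing, but the published text does not say whether that stop is recorded as due to an AE, as lack of efficacy, or as required by protocol.

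**Working it through.** There is no planned figure to reproduce: the documents give no AE, flare or discontinuation rate, and no precision or power statement for safety is visible. All rates below are assumptions chosen to show the mechanism.

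**Any AE.** Let *o* be the proportion with a non-AD AE and *f* the proportion with AD worsening. If the two are independent within an arm, P(any AE) = 1 − (1 − *o*)(1 − *f*).

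First set: *o* = 30% placebo, 45% drug (true excess +15 points).

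| Flares, placebo / drug | Any AE, placebo | Any AE, drug | Visible excess |
|---|---|---|---|
| 20% / 5% | 1 − 0.70 × 0.80 = 44.0% | 1 − 0.55 × 0.95 = 47.75% | +3.75 |
| 30% / 10% | 1 − 0.70 × 0.70 = 51.0% | 1 − 0.55 × 0.90 = 50.5% | −0.5 |
| 20% / 20% | 44.0% | 1 − 0.55 × 0.80 = 56.0% | +12 |

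The last row shows that equal flare rates only dilute: the excess becomes (1 − *f*) × 15 = 0.80 × 15 = 12.

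Second set: *o* = 40% placebo, 60% drug (true excess +20), with drug flares at 10%, so any AE on drug is 1 − 0.40 × 0.90 = 64%.

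- Placebo flares 20%: 1 − 0.60 × 0.80 = 52%, excess +12.
- Placebo flares 30%: 1 − 0.60 × 0.70 = 58%, excess +6.
- Placebo flares 40%: 1 − 0.60 × 0.60 = 64%, excess 0.
- Placebo flares 50%: 1 − 0.60 × 0.50 = 70%, excess −6.

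The excess vanishes when placebo flares reach 1 − 0.40(1 − *f* on drug)/0.60, which is 33%, 40% or 47% for drug flare rates of 0%, 10% or 20%.

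**Dependence.** Independence matters. If everyone who flares would have had another AE anyway, the first set gives 30% against 45%, and the full +15 remains.

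**Discontinuation due to AEs.** Assume AE-driven stops of 2% on placebo and 10% on drug (true excess +8), rescue-triggered stops of 10% and 3%, independence, and a share *s* of rescue stops recorded as due to an AE.

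- *s* = 0: 2% against 10%, excess +8.
- *s* = 0.5: 1 − 0.98 × 0.95 = 6.9% against 1 − 0.90 × 0.985 = 11.35%, excess +4.45.
- *s* = 1: 1 − 0.98 × 0.90 = 11.8% against 1 − 0.90 × 0.97 = 12.7%, excess +0.9.

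So any effect on this endpoint comes entirely from *s*, which the published text does not fix.

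**The case against.** A reader might infer that lack of efficacy on placebo enters both primary endpoints. The documents do not support that reading, for two reasons. Disease that persists without worsening falls under the exclusion in 10.3.2 and is not an AE. And 7.1 lists the systemic-rescue stop apart from the AE-based stop, with no visible rule that it is due to an AE. Both corrections stand.

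Other points against:

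- **No test is distorted.** The safety analysis is descriptive, and escalation under 4.1.1 and 6.6 also uses examinations, vital signs, injection-site reactions, laboratory tests and ECGs, with joint judgement by investigator and sponsor. This is true and limits the consequence. But descriptive rates are all that the primary analysis will report.
- **The expected toxicities are identifiable.** Section 4.2.1.1 names cutaneous and injection-site reactions, eosinophilia and dyspnea, and a flare term would not hide these. That protects the known signals, not the overall participant-level rate.
- **Excluding AD terms could remove drug effects.** Cutaneous findings are the most common adverse findings with the drug, and some could be coded as AD worsening. This stands, and is why the all-events summary must remain primary.
- **The AE window may work the other way.** Under 8.4.1, reporting runs to about 84 days after cessation. Placebo participants stopped early by the rescue rule might be observed for a shorter time, which would lower the placebo AE count. The net direction is therefore not certain.
- **Text is not shown.** The rescue text in 6.5.1, the stopping criteria in 6.6.1, the population definitions in 9.5 and parts of 9.6 are missing from the public document. The point concerns the published text only.
- **Numbers by dose are small.** An expansion panel holds at most 16, so one participant is at least 1/16, or about 6 points. Rows by dose will be coarse, which is a reason to add a pooled comparison.

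**Conclusion.** The point holds for the any-AE endpoint. AD worsening is an AE without exception, the visible analysis does not separate it, and a placebo excess of flares would narrow the contrast that placebo is there to provide. For discontinuation due to AEs it holds only conditionally, and the firm finding there is a missing classification rule.

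The size is unknown. In the assumed examples a true +15 points shows as +3.75 or −0.5 under independence, and as +15 under full overlap. Masking needs more flares on placebo than on drug, and enough participants whose only AE is a flare. This is an inexpensive improvement to the safety summary, not a flaw that invalidates the primary analysis.

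**What to change.** In Section 9.6:

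1. Keep the all-events summary as the primary presentation.
2. Add, by dose and for pooled active against placebo, the number and percentage of participants with any AE excluding AD worsening, and with discontinuation due to an AE excluding AD worsening.
3. Fix the list of excluded preferred terms before unblinding. Keep injection-site and other skin reactions off that list.
4. State, for the analysis, whether a stop triggered by systemic rescue or phototherapy counts as discontinuation due to an AE, and show such stops on their own line in either case.
5. Bring the primary endpoint list in 9.4 into line with Section 3.

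The cost is a few extra table rows, a short term list and one classification sentence. No new data are needed. AE recording and the clinical rules stay as they are.
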